7.2.5 Sponsor Responsibility for Reporting Adverse Events

All Adverse Events will be reported to regulatory authorities, IRB/IECs and investigators in accordance with all applicable global laws and regulations.

8.0 STATISTICAL ANALYSIS PLAN

This section outlines the statistical analysis strategy and procedures for the study. If, after the study has begun, changes are made to primary and/or key secondary hypotheses, or the statistical methods related to those hypotheses, then the protocol will be amended (consistent with International Conference on Harmonisation (ICH) Guideline E-9). Changes to exploratory or other non-confirmatory analyses made after the protocol has been finalized, along with an explanation as to when and why they occurred, will be listed in the Clinical Study Report (CSR) for the study. Post hoc exploratory analyses will be clearly identified in the CSR. No separate Statistical Analysis Plan (SAP) for the primary, secondary and exploratory endpoints will be issued for this study, however, a separate molecular profiling analysis plan will be developed to explicitly address exploratory biomarker objectives.

8.1 Statistical Analysis Plan Summary

This section contains a brief summary of the statistical analyses for this trial. Full detail is in the Statistical Analysis Plan (SAP) (Section 8.2).

8.1.1 Efficacy Analyses

The primary and key secondary endpoints, primary analysis population, and statistical methods that will be employed for the efficacy analyses are presented in [Table 10](#) below.

The primary hypothesis will be evaluated separately in each disease indication by evaluating best ORR by RECIST 1.1. A sequential monitoring approach will be used following the time that a minimum of 6 subjects have had at least 1 post-baseline scan in each indication.

The Type-I error rate over the multiple evaluations within an indication will be controlled by the truncated sequential probability ratio test procedure at 0.08 (1-sided) [32].

Table 10 Summary of Analysis Strategy for Key Efficacy Endpoints

Endpoint/Variable (Description, Timepoint)	Statistical Method	Analysis Population	Missing Data Approach
Primary Hypothesis #1:			
Best ORR by RECIST 1.1 in each disease indication	Truncated sequential probability ratio test [32]	Full Analysis Set (FAS)	Missing observation counted as non-responder
Secondary Objectives – Within Indication			
PFS	Summary statistics using Kaplan-Meier method	FAS	Censored at last assessment
OS	Kaplan-Meier method	FAS	Censored at last assessment
DOR	Summary statistics using Kaplan-Meier method	All responders	Non-responders are excluded in analysis

8.1.2 Safety Analyses

The All-Subjects-as-Treated population will be employed for safety analyses. Immune related adverse experiences are prespecified as events of interest.

8.1.3 Power and Sample Size

Within each indication, the study will enroll a minimum of 6 subjects. Following the time that at least 6 subjects have had at least 1 post-baseline response assessment, a sequential monitoring procedure will be used to evaluate for efficacy and futility simultaneously based on the number of subjects with a confirmed or unconfirmed response according to the rules outlined in [Figure 2](#), [Table 11](#), and [Table 12](#).

Depending on the enrollment rate, it is possible that more than 6 subjects may be enrolled prior to the first evaluation of efficacy or futility. Enrollment is expected to be continuous and will not be held within an indication.

Once at least 6 subjects are evaluable for confirmed or unconfirmed response, subsequent rules for pausing enrollment and future evaluations will be based on the boundaries identified by the sequential monitoring procedure. Approximately 22 subjects will be enrolled in each indication. The total sample size is approximately 440 subjects. Further details are provided in Section 8.2.7.

With 22 subjects per indication, this study provides 80% power to demonstrate that the best ORR induced by pembrolizumab exceeds 10% at an overall one-sided 8% alpha-level, if the true best ORR within an indication is 35%. The underlying treatment effect is regarded as clinically important in each of the indications studied. The calculation is based on the

binomialSPRT function in the gsDesign package and is carried out using R. The minimum criterion for success is that the lower bound of the repeated CI > 10% [33]. Given the underlying true rate, this may occur when at least 6/22 subjects develop a response. Further details are provided in Section 8.2.7.

[figure not shown]

Figure 2 Sequential Monitoring Rules for Efficacy and Futility

Table 11 Decision Rules Based on Efficacy Bounds

Monitoring Point (# Subjects)	Minimum # Responders to Start Future Study Planning
6-7	3
8-12	4
13-17	5
18-22*	6
23-26	7
27-30	8
Design assumes overall Type I error of 8% (1-sided) and 80% power. *Success at the final analysis requires $\geq 6/22$ subjects with a response.	

Table 12 Decision Rules Based on Futility Bounds

Monitoring Point (# Subjects)	Maximum # Subjects with Response to Declare Futility
6-9	0
10-14	1
15-19	2
20-24*	3
25-28	4
29-30	5
Design assumes overall Type I error of 8% (1-sided) and 80% power. *Success at the final analysis requires $\geq 6/22$ subjects with a response.	

8.1.4 Interim Analysis

Multiple interim analyses may be performed in this study due to the sequential design of the trial. Results will be reviewed by the study team. The endpoint(s), timing, and purpose of the interim analysis are summarized in the [Table 13](#). The decision rule and other statistical details are further described in Section 8.2.9.

Table 13 Summary of Interim Analysis Strategy

Key Endpoints for Interim Analysis	Timing of Interim Analysis	Purpose of Interim Analysis
Objective response rate (confirmed or unconfirmed)	Sequential monitoring approach	
• Stop for futility• Go to future study planning

8.2 Statistical Analysis Plan

8.2.1 Responsibility for Analyses/In-House Blinding

The statistical analysis of the data obtained from this study will be the responsibility of the Clinical Biostatistics department of the Sponsor.

This trial is being conducted as an open-label study, i.e., subjects, investigators, and Sponsor personnel will be aware of subject treatment assignments after each subject is enrolled and treatment is assigned.

The Clinical Biostatistics department will generate the allocation schedule(s) for study treatment assignment. Allocation will be implemented in an interactive voice response system (IVRS).

8.2.2 Hypotheses/Estimation

Objectives and hypotheses of the study are stated in Section 3.0.

8.2.3 Analysis Endpoints

Efficacy and safety endpoints that will be evaluated for within- and/or between-treatment differences are listed below, followed by the descriptions of the derivations of selected endpoints.

8.2.3.1 Efficacy Endpoints

Efficacy endpoints that will be evaluated for are listed below, followed by the descriptions of the derivations of selected endpoints.

The primary efficacy endpoint is best ORR, defined as the proportion of subjects in the analysis population who have CR or PR based on assessments by the investigator, and confirmed per RECIST 1.1 at any time during the study. Response for the primary analysis will be determined by the investigator assessment, and a confirmation assessment is required per RECIST 1.1.

Secondary efficacy endpoints include: (1) DOR, defined as time from first RECIST 1.1 response to disease progression in subjects who achieve a PR or better based on assessments by the investigator, and confirmed per RECIST 1.1; (2) PFS, defined as the time from allocation to the first documented disease progression based on assessments by the

investigator, and confirmed per RECIST 1.1 or death due to any cause, whichever occurs first; and (3) OS, defined as the time from first dose of trial medication to the time of death due to any cause.

Additional supportive analyses of best ORR, DOR, and PFS will be conducted using modified RECIST 1.1 criteria, in which a confirmation assessment of disease progression must be obtained at least 4 weeks after the initial disease assessment indicating progressive disease.

8.2.3.2 Safety Endpoints

A description of safety measures is provided in Section 4.2.3.2.

The primary safety endpoints are AEs graded using CTCAE (Version 4.0) criteria. Safety will be assessed by quantifying the toxicities and grades experienced by subjects who have received pembrolizumab, including SAEs and ECIs. Immune related adverse experiences (irAEs) are prespecified as events of interest. Other safety endpoints include laboratory safety assessments, ECOG performance status, vital signs and physical examinations.

8.2.4 Analysis Populations

8.2.4.1 Efficacy Analysis Populations

The FAS population will serve as the primary population for the analysis of efficacy data in this study. The FAS population consists of all subjects within each indication who:

- Receive at least 1 dose of study treatment, and
- Have a baseline scan with measurable disease per RECIST 1.1

Subjects will be included in the treatment group to which they are allocated for the analysis of efficacy data. Details on the approach to handling missing data are provided in Section 8.2.5, Statistical Methods.

8.2.4.2 Safety Analysis Populations

The All Subjects as Treated (ASaT) population will be used for the analysis of safety data in this study. The ASaT population consists of all allocated subjects who received at least 1 dose of study treatment.

At least 1 laboratory or vital sign measurement obtained subsequent to at least 1 dose of study treatment is required for inclusion in the analysis of each specific parameter. To assess change from baseline, a baseline measurement is also required.

Details on the approach to handling missing data for safety analyses are provided in Section 8.2.5, Statistical Methods.

8.2.5 Statistical Methods

Statistical testing and inference for safety analyses are described in 8.2.5.2. Efficacy results that will be considered to be statistically significant after consideration of the strategy for controlling the Type I error are described in Section 8.2.6, Multiplicity. Nominal p-values may be computed for other efficacy analyses as a measure of strength of association between the endpoint and the treatment effect rather than formal tests of hypotheses. Unless otherwise stated, all statistical tests will be conducted at the $\alpha=0.05$ (2-sided) level.

8.2.5.1 Statistical Methods for Efficacy Analyses

Efficacy will be evaluated separately in each cohort. For the primary efficacy endpoint investigator assessed RECIST 1.1 best ORR, the point estimate, repeated confidence interval, and adjusted p-value for testing the RECIST 1.1 response rate is greater than 10% for each disease indication will be provided using a truncated sequential probability ratio test [32], which is a specific instance of an exact binomial group sequential design for a single arm trial with a binary outcome. Subjects in the primary analysis population (FAS) without response data will be counted as non-responder. Interim decisions may be made based on confirmed or unconfirmed response assessments (see Sections 8.2.7 and 8.2.9). However, the final analysis (if enrollment in a given indication expands to 22 subjects) will require a confirmation assessment for all subjects who develop a CR or PR.

For PFS endpoint, Kaplan-Meier (KM) curves and median estimates from the KM curves will be provided as appropriate. Subjects without efficacy evaluation data or without survival data will be censored at Day 1.

Table 14 summarizes the key efficacy analyses.

Table 14 Analysis Strategy for Key Efficacy Variables

Endpoint/Variable (Description, Time Point)	Primary vs. Supportive Approach [†]	Statistical Method	Analysis Population	Missing Data Approach
Primary Hypothesis #1 – Within Indication				
Best ORR using RECIST 1.1 by site radiology assessment (each disease indication evaluated separately)	P	Truncated sequential probability test	FAS	Subjects with missing data are considered non-responders
Best ORR using modified RECIST 1.1 by site radiology assessment (each disease indication evaluated separately)	S	Truncated sequential probability test	FAS	Subjects with missing data are considered non-responders
Secondary Endpoints/Objectives – Within Indication				
PFS using RECIST 1.1 criteria by site assessment	P	Summary statistics using Kaplan-Meier method	FAS	Censored at last assessment
PFS using modified RECIST 1.1 criteria by site assessment	S	Summary statistics using Kaplan-Meier method	FAS	Censored at last assessment
OS	P	Kaplan-Meier method	FAS	Censored at last assessment
DOR by site assessment	P	Summary statistics using Kaplan-Meier method	All responders	Non-responders are excluded in analysis
Duration of modified RECIST 1.1 response (DOR) by site assessment	S	Summary statistics using Kaplan-Meier method	All modified RECIST 1.1 responders	Non-responders are excluded in analysis
† P=Primary approach; S=Secondary approach.				

The strategy to address multiplicity issues with regard to multiple efficacy endpoints is described in Section 8.2.6, Multiplicity and Section 8.2.9, Interim Analyses.

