RECIST 1.1 will be adapted as described in Section 4.2.3.1 due to the tumor response patterns seen with pembrolizumab treatment (e.g., tumor flare), and this adapted RECIST will be used by the sites for treatment decisions. Adverse events (AEs) will be monitored throughout the trial and graded in severity according to the guidelines outlined in the National Cancer Institute (NCI) Common Terminology Criteria for Adverse Events (CTCAE) version 4.0. Treatment with pembrolizumab will continue until documented disease progression, unacceptable AEs, intercurrent illness that prevents further administration of treatment, investigator's decision to withdraw the subject, subject withdraws consent, pregnancy of the subject, noncompliance with trial treatment or procedure requirements, completion of 24 months of treatment with pembrolizumab, or administrative reasons. Subjects who attain an investigator-determined confirmed complete response (CR) may consider stopping trial treatment after receiving at least 24 weeks of treatment. In addition, subjects who discontinue after at least 24 months of therapy for reasons other than disease progression or intolerability, or who discontinue after attaining a CR and had at least 2 treatments beyond initial CR, may be eligible for up to 1 year of retreatment if they subsequently experience radiographic disease progression. The decision to retreat will be at the discretion of the investigator only if no cancer treatment was administered since the last dose of pembrolizumab, the subject still meets the safety parameters listed in the Inclusion/Exclusion criteria and the trial remains open (refer to Section 7.1.5.2.1 for further details). After the end of treatment, each subject will be followed for 30 days for adverse event monitoring (serious adverse events will be collected for 90 days after the end of treatment). Subjects who discontinue treatment for reasons other than disease progression will have post-treatment follow-up of disease status until disease progression, initiating a non-study cancer treatment, withdrawing consent, or becoming lost to follow-up. All subjects will be followed by telephone contact for overall survival (OS) until death, withdrawal of consent or the end of the study, whichever comes first.

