^d Note: Subjects with prostate cancer who are currently on luteinizing-hormone-releasing hormone (LHRH) analogs and breast cancer subjects receiving LHRH analogs for ovarian suppression to avoid menses are eligible for this study and may continue to take the LHRH analogs while participating in this study.

5. Have provided tissue for biomarker analysis from an archival tissue sample or newly obtained core or excisional biopsy of a tumor lesion not previously irradiated (tumors progressing in a prior site of radiation are allowed for PD-L1 characterization, other exceptions may be considered after Sponsor consultation).
6. Have a PD-L1 positive tumor as determined by IHC at a central laboratory from either an archived formalin-fixed, paraffin embedded (FFPE) tumor sample or a newly obtained biopsy.
7. Have measurable disease based on RECIST 1.1. Tumor lesions situated in a previously irradiated area are considered measurable if progression has been demonstrated in such lesions.
8. Have a performance status of 0 or 1 on the ECOG Performance Scale.
9. Demonstrate adequate organ function as defined in [Table 1](#), all screening labs should be performed within 10 days of treatment initiation.

Table 1 Adequate Organ Function Laboratory Values

System	Laboratory Value
Hematological	
Absolute neutrophil count (ANC)	≥1,500 /mCL
Platelets	≥100,000 / mCL
Hemoglobin	≥9 g/dL or ≥5.6 mmol/L
Renal	
Creatinine OR Measured or calculated ^a creatinine clearance (GFR can also be used in place of creatinine or CrCl ^a)	≤1.5xULN OR ≥60 mL/min for subject with creatinine levels >1.5x institutional ULN
Hepatic	
Total bilirubin	≤1.5xULN OR Direct bilirubin ≤ULN for subjects with total bilirubin levels >1.5xULN
AST (SGOT) and ALT (SGPT)	≤2.5xULN OR ≤5xULN for subjects with liver metastases
Coagulation	
International Normalized Ratio (INR) or Prothrombin Time (PT)	≤1.5xULN unless subject is receiving anticoagulant therapy as long as PT or PTT is within therapeutic range of intended use of anticoagulants
Activated Partial Thromboplastin Time (aPTT)	≤1.5xULN unless subject is receiving anticoagulant therapy as long as PT or PTT is within therapeutic range of intended use of anticoagulants
^a Creatinine clearance (CrCl) should be calculated per institutional standard. ALT (SGPT)=alanine aminotransferase (serum glutamic pyruvic transaminase); AST (SGOT)=aspartate aminotransferase (serum glutamic oxaloacetic transaminase); GFR=glomerular filtration rate; ULN=upper limit of normal.	

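### Read literally, the PFS censoring sentence in section 8.2.5.1 censors at Day 1 a treated subject who dies with no post-baseline scan, although section 8.2.3.1 counts that death as a PFS event.

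*Combined protocol and SAP*

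**What the plan says.** Section 8.2.5.1, directly after announcing Kaplan-Meier curves and medians for PFS, states: "Subjects without efficacy evaluation data or without survival data will be censored at Day 1".

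Section 8.2.3.1 defines the PFS event as progression, "confirmed per RECIST 1.1 or death due to any cause, whichever occurs first".

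The FAS in section 8.2.4.1 has two conditions: "Receive at least 1 dose of study treatment, and" a baseline scan showing measurable disease. It does not ask for a post-baseline scan.

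Deaths should be known, because section 2.1 says "All subjects will be followed by telephone contact for overall survival (OS) until death".

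For PFS, the missing-data column of Tables 10 and 14 reads only "Censored at last assessment".

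Section 8.0 adds that "No separate Statistical Analysis Plan (SAP) for the primary, secondary and exploratory endpoints will be issued for this study".

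**The concern.** The two conditions in the censoring sentence are alternatives, so lacking efficacy evaluation data is enough by itself to trigger censoring at Day 1. A subject who is dosed and dies before the first post-baseline scan meets that condition, belongs to the FAS and has a known date of death. The endpoint definition counts an event on that date. The censoring sentence removes the subject from the risk set at the start.

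If the censoring sentence is applied as written, it discards the earliest deaths, which are the least favourable PFS outcomes. For deaths before the first scan time this raises every later point of the curve. For a subject who is never scanned and dies late, the effect can go the other way. Two analysts working from the same data could report different PFS curves, each citing the plan.

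The stakes are limited. PFS is a secondary objective assessed separately in each of 20 indications, without a hypothesis or decision rule.

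**Working it through.** **Reading the text.** The plan does not define efficacy evaluation data. If a baseline scan counted, no FAS subject could lack such data and the clause would be empty, so I take it to mean post-baseline assessments. The first scheduled scan is at 56 ± 7 days (section 7.1.2.5.3), so a death can precede it. Tables 10 and 14 do not cover a subject who dies with no assessment, and no other section exempts deaths from the sentence.

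**Inputs.** The plan states no PFS figure, so there is none to reproduce. n = 22 per cohort comes from section 8.1.3. Everything else is assumed: d deaths at week 5 without a scan, p progressions at week 8, 5 progressions at week 16, the rest censored at week 24. Day 1 is time zero.

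**General effect.** With deaths as events, the curve just before week 8 is (22−d)/22. With Day 1 censoring it is 1. The risk set at week 8 is 22−d under both rules, so every later factor is identical, and the ratio of literal to defined PFS from week 8 onward is 22/(22−d).

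| d | PFS before week 8, deaths as events | PFS before week 8, Day 1 censoring | Ratio from week 8 |
|---|---|---|---|
| 1 | 21/22 = 0.955 | 1.000 | 22/21 = 1.048 |
| 2 | 20/22 = 0.909 | 1.000 | 22/20 = 1.100 |
| 3 | 19/22 = 0.864 | 1.000 | 22/19 = 1.158 |
| 4 | 18/22 = 0.818 | 1.000 | 22/18 = 1.222 |

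**Examples.** S(8) is (22−d−p)/22 with deaths as events and (22−d−p)/(22−d) with Day 1 censoring.

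| d, p | S(8), deaths as events | S(8), Day 1 censoring | Median (weeks) |
|---|---|---|---|
| 2, 8 | 12/22 = 0.545 | 12/20 = 0.600 | 16 and 16 |
| 3, 9 | 10/22 = 0.455 | 10/19 = 0.526 | 8 and 16 |
| 4, 8 | 10/22 = 0.455 | 10/18 = 0.556 | 8 and 16 |

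For d = 3 and p = 9, S(16) is 5/22 = 0.227 against 5/19 = 0.263.

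**Median over a grid.** Taking d = 1 to 4 and p = 5 to 11 gives 4 × 7 = 28 cells. The median is unchanged in 18. It moves without a tie in 2, namely (d, p) = (3, 9) and (4, 8). In the other 8, survival is exactly 0.500 under one of the rules at the deciding time, so the answer depends on the convention for ties: (1,5), (1,10), (2,5), (2,9), (2,10), (3,8), (4,7) and (4,9).

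**Opposite direction.** Suppose one never-scanned subject dies at week 60, 11 progress at week 8, 5 at week 16, and 5 are censored at week 24. With the death as an event, S(8) = 11/22 = 0.500 and S(16) = 6/22 = 0.273. With Day 1 censoring, S(8) = 10/21 = 0.476 and S(16) = 5/21 = 0.238.

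**The case against.** The strongest reply is that the two sections do different jobs. Section 8.2.3.1 defines events; the censoring sentence and the tables deal with missing data. A known death is an observation, and the usual practice is to assign events first and censor only those without one. Read in that order, the sections give one answer and the death counts. A related argument is that death is a component of PFS, so a recorded death is itself efficacy evaluation data.

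The second argument fails because the sentence lists survival data separately from efficacy evaluation data. The first describes good practice, but the plan does not state that order, and the sentence as written has no exception for a subject with an event. It does show that the divergence arises only if an analyst lets the sentence override the definition and such a subject exists.

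Other parts of the objection stand. The intended meaning was probably neither kind of data, which agrees with section 8.2.3.1. The number of unscanned deaths is assumed throughout, and the plan has features that keep it low: entry requires subjects to "Have a performance status of 0 or 1 on the ECOG Performance Scale", scans may be done early if clinically indicated, and one is due at treatment discontinuation. The late-death example is remote, since it needs a treated subject who is never scanned in 60 weeks.

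Section 8.0 also requires "Changes to exploratory or other non-confirmatory analyses made after the protocol has been finalized" to be listed in the study report. That discloses a change afterwards; it does not fix the rule beforehand.

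**Conclusion.** The concern holds as a point about the literal text, and it is minor. The stated rule censors at Day 1 a death that the endpoint definition counts, and nothing else in the plan resolves the difference.

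The effect is usually to raise reported PFS. Under the assumptions of n = 22, 1 to 4 unscanned deaths before the first scan and no other early censoring, the increase from the first scan onward is about 5% to 22% in relative terms. In the worked examples S(8) rises by 5.5 to 10.1 percentage points. The median would usually not change; the two untied shifts need 3 or 4 of 22 subjects to die unscanned.

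The primary analysis is unaffected, because FAS subjects without response data already count as non-responders there. The interim rules and the success criterion do not use PFS.

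**What to change.** Replace the sentence in section 8.2.5.1 with wording such as:

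> A subject with no post-baseline tumour assessment and no recorded death is censored at Day 1. A death without prior documented progression, including one with no post-baseline assessment, is a PFS event on the date of death. A subject with assessments but neither progression nor death is censored at the last assessment.

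This matches section 8.2.3.1 and Tables 10 and 14. It also drops the undefined term for survival data, which on one reading could send a scanned subject to Day 1 instead of the last assessment.

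The cost is one sentence, with no new data and no change to the primary analysis. Reported PFS may come out slightly different, usually less favourable. A never-scanned subject who dies late would count as progression-free until death, which can raise PFS, but the existing definition already implies that. The change should be made before PFS is analysed.
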